7.2.4 Efficacy analysis

7.2.4.1 Primary endpoint and analysis method

[Primary endpoint]

Progression-free survival (PFS rate) at 6 months after enrollment

The PFS rate 6 months after enrollment, the primary endpoint, is the gross proportion of surviving subjects without documented progression up to 6 months after enrollment (date of enrollment + 24 weeks \pm 2 weeks), counting from the day of enrollment. Subjects with no imaging data on progression at 6 months after enrollment and subjects lost to follow-up will be included in the denominator, but will not be handled as progression-free.

Definition of progression:

Progression will include both progressive disease (PD) based on diagnostic imaging assessed according to RECIST ver. 1.1 and primary disease progression that cannot be confirmed by diagnostic imaging (clinical progression). When progression is documented by diagnostic imaging, the day on which the diagnostic imaging is performed will be the progression date. For clinical progression, the day of the clinical determination will be the progression date. In a case in which, for example, tumor diameter has become extremely small, if the status is determined to be “not definite progression” clinically, although the assessment is PD according to the response criteria, the assessment of PD according to the response criteria will take precedence and the status will be considered progression. (In this case, the clinical determination on continuing protocol treatment will take precedence.) Even if the assessment is not PD according to the response criteria, if there is

definite clinically documented progression, the clinical determination will take precedence and the status will be considered progression. For surviving subjects without documented progression, the period will be cut off on the final day when a progression-free status is confirmed (final day of progression-free survival confirmation). Confirmation of progression-free status by imaging test or sample test is not mandatory, and clinical confirmation by outpatient medical examination, etc., will be allowed. Contact by telephone only will not be allowed. Events and the cut-off will also be handled the same way in subjects who have discontinued protocol treatment for reasons such as toxicity and refusal of treatment, even if another (follow-up) therapy is added. Thus, the time of treatment discontinuation or the day of follow-up treatment initiation will not be the cut-off.

[Main analysis]

The following analysis will be performed on the “full analysis set.”

PFS rate at 6 months is calculated by counting of subjects with progression, without progression, and unconfirmed at 6 months. Based on the observed PFS rate at 6 months from the day of enrollment, binomial test will be conducted on the null hypothesis “value will be determined invalid at PFS rate $\leq 29\%$.” Significant level will be 2.5% (one-sided) in the main analysis. For interval estimation, accurate 90% confidence interval (two-sided) based on binomial distribution will be used.

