- *6: Test results from up to one year before obtaining consent may be used. It is unnecessary to record this in the CRF. However, follow JSH Guidelines for the Management of Hepatitis B virus infection for the measurement of HBs antibody, HBc antibody and HBV-DNA.
- *7: If done within 14 days before enrollment, results from before obtaining informed consent may be used.
- *8: If it has been performed within 28 days before treatment day, the test for Course 1 may be omitted.
- *9: Measure once every 8 weeks (56 days) with Day 1 of Course 1 as starting point. However, reduce the frequency to once every 12 weeks (84 days) when one year has passed since initiation of protocol treatment.
- *10: Imaging test will be performed within 4 weeks (28 days) prior to enrollment (including the same day of week as the day of enrollment). The results of imaging diagnosis/test performed before obtaining consent may be used if it is performed within 4 weeks (28 days) prior to enrollment.
- *11: This is only done when discontinuation is for a reason other than imaging results (PD).

Table 9.c Allowance range for protocol treatment and laboratory tests

Performed items	Protocol specification	Allowance range
Clinical Laboratory test values (During protocol treatment)	Course 1: Day 1, 8, 15, 22 (phase I part of the study) or Day 1, 15, 22 (phase II part of the study) Course 2: Day 1, 15	From Day -2 before scheduled day (However, Mg is tested once per course.)
Protocol treatment	Day 1, 15, 29 (Day 29 is equal to Day 1 of next course)	Scheduled day \pm 3 days
Tumor markers and imaging tests (during protocol treatment)	Protocol treatment \leq 1 year: 8 weeks (56 days)	Scheduled day \pm 1 week (7 days)
	Protocol treatment > 1 year: 12 weeks (84 days)	Scheduled day \pm 2 week (14 days)

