9.2.10 Imaging test (thoracoabdominal-pelvic CT/MRI)

Imaging test will be performed within 4 weeks (28 days) prior to enrollment (including the same day of week as the day of enrollment). The results of imaging diagnosis/test performed before obtaining consent may be used if it is performed within 4 weeks (28 days) prior to enrollment.

Furthermore, the data of measurable lesion should be evaluated with imaging test conducted within 2 weeks (14 days) prior to initiation of protocol treatment (including the same day of week as the day of enrollment) preferably. If another imaging test has been conducted newly after enrollment but before initial administration, this data should be recorded in CRF.

After initiation of protocol treatment, imaging test will be performed every 8 weeks (56 days) with protocol treatment initiation date (Day 1) of Course 1 as the starting point. However, when 1 year has passed since initiation of protocol treatment, imaging may be performed once every 12 weeks (84 days), counting from the point in time at which 1 year has passed. (For details, see “Table 9.a Study calendar (phase I part of the study)” or “Table 9.b Study calendar (phase II part of the study).”

Thoracoabdominal-pelvic CT (in principle, contrast CT; a slice width of 5 mm or less is recommended, but MRI is also acceptable) will be used for imaging test, and the modality and the date of imaging test will be entered into the CRF. If necessary, brain MRI / CT and a neck CT will be performed.

In principal, the same modality should be used for imaging test during protocol treatment throughout the study period.

The investigator or the subinvestigator should evaluate the test results according to the RECIST v1.1 (see Appendix A) and enter the determined results into the CRF.

Furthermore, for subjects withdrawn from the study for any reason other than imaging test results such as clinical PD, imaging test specified at the time of discontinuation should be performed within 4 weeks (28 days) including the day of decision (including the same day of week as the day of decision).

If the subject is not determined to have PD on imaging up to the time of withdrawal, the following information should be collected until the subject dies or the sponsor terminates the study, even after follow-up treatment has been started.

- Day of decision on clinical PD (only when the subject is not determined to have clinical PD by the time of discontinuation)

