13.3.3 Efficacy analysis

13.3.3.1 Primary endpoint and analysis method

[Primary endpoint]

PFS rate 6 months after enrollment

The PFS rate 6 months after enrollment, the primary endpoint, is the gross proportion of surviving subjects without documented progression up to 6 months after enrollment, counting from the day of

CONFIDENTIAL

enrollment. Subjects with no imaging data on progression at 6 months after enrollment and subjects lost to follow-up will be included in the denominator, but will not be handled as progression-free.

The criteria for determining progression are described in “13.3.3.2 Secondary Endpoints and Analytical Methods for Them”.

[Main analysis]

The following analysis will be performed in the “full analysis set”.

PFS rate at 6 months is calculated by counting of subjects each subjects with progression, not progression, or unconfirmed at 6 months. “At 6 months” in the main analysis is defined as 24 weeks (8 weeks x 3) with time window of 2 weeks before and after. Based on the observed PFS rate at 6 months from the day of enrollment, binomial test will be conducted on the null hypothesis “value will be determined invalid at PFS rate $\leq 29\%$ ”. Significant level will be 2.5% (one-sided) in main analysis. For interval estimation, accurate 90% confidence interval (two-sided) based on binomial distribution will be used.

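### Read literally, the primary-endpoint window closes on enrollment day 182, so a progression-free subject whose on-schedule third scan falls on days 183–189 counts as a failure

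*SAP*

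**What the plan says.** SAP v4.0, 7.2.4.1, counts the primary endpoint from enrollment: surviving subjects "without documented progression up to 6 months after enrollment (date of enrollment + 24 weeks" plus or minus 2 weeks. Protocol 13.3.3.1 sets the same width; six months "is defined as 24 weeks (8 weeks x 3) with time window of 2 weeks before and after".

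The missing-imaging rule, in both documents, is strict. "Subjects with no imaging data on progression at 6 months after enrollment and subjects lost to follow-up will be included in the denominator", and they are not treated as progression-free. The main analysis then rests on "counting of subjects with progression, without progression, and unconfirmed at 6 months"; unconfirmed is not defined.

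Scans run on another clock. Under Protocol 9.2.10, "imaging test will be performed every 8 weeks (56 days) with protocol treatment initiation date (Day 1) of Course 1 as the starting point". Table 9.c, in the row for "Tumor markers and imaging tests (during protocol treatment"), allows 7 days either side in the first year. Protocol 7.3.1 and 8.1 ask for treatment to start within 14 days of registration, in 8.1 only in principle; 7.3.1 requires a report to the study office only when the start falls beyond 4 weeks.

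Two pieces of text pull the other way. Within its definition of progression, SAP 7.2.4.1 says: "Confirmation of progression-free status by imaging test or sample test is not mandatory", and it accepts a clinical examination instead. Protocol 6.2.2.2 and the synopsis word the tested rate as 6 months from start of treatment, and SAP section 3 times the initial analysis from start of treatment.

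**The concern.** Enrollment and treatment start can differ by two weeks or more. The endpoint window follows one and the scan calendar follows the other, so a site can keep to the protocol and still produce a third scan after the window has closed. No other scheduled scan can stand in for it. A subject known to be progression-free at that scan would then lower the success count.

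At stake is the power of the primary binomial test. The binary 6-month rate could also lie below the Kaplan-Meier 6-month rate for a reason unrelated to disease, and no planned analysis would show why.

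**Working it through.** **The plan's own figure.** Inputs from Protocol 6.2.2.2: threshold 29%, expected 48%, one-sided 5%, power 80%, 47 subjects needed, target 52. The exact binomial test at n=47 rejects at 20 or more successes, with actual level 0.0327 and power 81.4%. The planned 47 is reproduced. At n=52 the cut-off is 22, actual level 0.0278, power 83.2%. The 5% level is that of Protocol 13.3.3.4 and SAP 7.2.4.5; the 2.5% in the main-analysis text is a separate matter and is not used here.

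**Window.** 168 − 14 = 154 to 168 + 14 = 182 days from enrollment.

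**Third scan.** Let d be the treatment start (days after enrollment) and v the scan deviation (days).
- Scan day = 168 + d + v.
- For d = 0 to 14 and v = −7 to +7, this spans 161 to 189.
- It passes day 182 only if d + v > 14.
- A scan on its due day after a start within 14 days is never missed (168 + 14 = 182).
- A start by day 7 is never missed (168 + 7 + 7 = 182).
- A miss therefore needs a start on days 8–14 with a late scan, or a start after day 14. A start on day 28 allows scans to 168 + 28 + 7 = day 203.
- If Course 1 Day 1 is numbered Day 1 and the scan is due on Day 168, day 189 becomes day 188.

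**Other scans, starts within 14 days.** Scan 2 (112 + d + v) is at latest 112 + 14 + 7 = 133. Scan 4 (224 + d + v) is at earliest 224 − 7 = 217. Neither reaches days 154–182.

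**Share missed (s).** The documents give no distribution for d or v, so every non-zero value below is an assumption. Uniform d and v over the full allowed ranges gives 28 of 15 × 15 = 225 combinations, or 12.4%. Uniform d with v within 3 days gives 6 of 15 × 7 = 105, or 5.7%. The other rows take a Poisson start delay, with v uniform over the range shown.

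**Effect.** Power = P(X ≥ cut-off) with success probability 0.48(1 − s), taking misses as independent of outcome. Type I error uses 0.29(1 − s).

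| Assumed scenario | s | Power, n=52 | Power, n=47 |
|---|---|---|---|
| Start by day 14, scan on due day | 0% | 83.2% | 81.4% |
| Poisson mean 5, scan ±3 | 0.12% | 82.9% | 81.2% |
| Poisson mean 7, scan ±3 | 1.47% | 80.5% | 78.7% |
| Poisson mean 5, scan ±7 | 1.70% | 80.0% | 78.2% |
| Uniform 0–14, scan ±3 | 5.7% | 71.3% | 69.7% |
| Poisson mean 7, scan ±7 | 6.95% | 68.3% | 66.7% |
| Uniform 0–14, scan ±7 | 12.4% | 53.7% | 52.7% |

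Power falls below 80% once s exceeds about 1.7% at n=52 or about 0.8% at n=47. With 52 × 0.48 ≈ 25 expected progression-free subjects, s = 1.7% is 0.4 of a subject, 6.95% is 1.7 and 12.4% is 3.1. Type I error at n=52 falls from 0.028 to 0.012 at 6.95% and 0.006 at 12.4%.

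**Kaplan-Meier rates** (SAP 7.2.4.2 and 7.4). A subject with a clean scan on day 185 stays at risk past week 24, so these estimates do not change.

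**The case against.** The strongest reply is that the failure score is only one reading. A clean scan on day 185 is arguably imaging that shows no progression at 6 months. SAP 7.2.4.1 accepts clinical confirmation, and the 8 weeks × 3 in Protocol 13.3.3.1 echoes the scan cycle; counted from Course 1 Day 1, every permitted third scan (days 161–175) falls inside the window. This stands as evidence of conflict, but it does not remove the problem. The clinical-confirmation sentence follows the rule for cutting off PFS time, whereas the no-imaging rule is written for the primary endpoint, and SAP 7.2.4.1 anchors the window on enrollment in plain terms.

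It is also fair that the 2-week margin absorbs a 14-day start delay when scans are on time, that the SAP listings of response evaluations and PD determinations should identify affected subjects, and that the success rule of an open-label single-arm trial should not be loosened late. The window has been in the SAP since v2.0 (February 28, 2017). SAP v4.0 is dated July 10, 2018 and planned enrollment ended in March 2017, so on planned dates 6-month outcomes already existed by then. The timing point limits the remedy.

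A reader might infer that the effect is probably small. The count of subjects may well be, but the documents do not support that for power, because less than one missed subject on average takes it below 80%. Nor is it a general reassurance that three of the four Poisson scenarios keep 80% at n=52: at the required 47, only one does.

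**Conclusion.** The point holds as a defect in the stated rule. Read literally, the plan scores some progression-free subjects as failures although their scans were on schedule, and other wording in the plan contradicts that reading. It should be corrected, but it does not threaten the validity of a positive result, because the bias only lowers the success count.

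The size is uncertain: from no loss to about 3 of 25 progression-free subjects, with power between 83.2% and 53.7% at n=52, or 81.4% and 52.7% at n=47. These limits rest on assumed start delays and scan deviations, a start within 14 days in the uniform cases, and misses unrelated to outcome. A reader might infer that the trial is badly underpowered; the documents do not support that either, since nothing in them shows how often treatment started late or scans ran late.

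**What to change.** In Protocol 13.3.3.1 and SAP 7.2.4.1:

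- Keep enrollment as time zero and day 182 as the limit for counting progression (radiological or clinical) and death.
- Add that the scheduled third scan (Course 1 Day 1 + 168 ± 7 days), if it falls after day 182 and shows no PD, counts as the 6-month imaging. No scan beyond that allowance qualifies.
- Define unconfirmed as having no qualifying scan. Such a subject remains a failure, as does one whose late third scan shows PD.
- State that the clinical-confirmation sentence governs PFS censoring only.
- Report the count and test under the strict window as a sensitivity analysis.

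Align the start-of-treatment wording in Protocol 6.2.2.2 and the synopsis with the enrollment wording of the analysis sections, and reconcile the timing statement in SAP section 3 with it.

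Make the change before data fixation and without reference to the affected subjects' results. If the 6-month result has already been tabulated, keep the strict window as the main analysis and report the schedule-aligned count as the sensitivity analysis.

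The cost is wording and one extra count. No extra scans are needed, since under Protocol 9.2.10 "the modality and the date of imaging test will be entered into the CRF". The downsides are a slightly less strict rule and a short wait for late third scans.

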As increased anti-tumor effect can be expected by using TAS-102 in combination with panitumumab treatment which is the standard treatment for patients with unresectable, advanced/recurrent colorectal cancer, the PFS rate at 6 months in this study was assumed to be 48% and this was set as the expected value for the panitumumab treatment in combination with TAS-102 therapy in patients with RAS wild-type unresectable, advanced/recurrent colorectal cancer. *Also, for the threshold where* further development for panitumumab treatment in combination with TAS-102 may be considered not necessary, it was assumed to be 29% from the CI lower limit of the PFS rate at 6 months in the ASPECCT study.¹⁷⁾

For the main analysis, based on the observed PFS rate at 6 months from start of treatment, binomial test will be conducted on the null hypothesis “the true PFS rate at 6 months from start of treatment will be not more than the PFS threshold rate where value is determined invalid”. With the PFS threshold rate at 29%, PFS expected rate at 48% at 6 months from start of treatment, and one-sided significant level at 5%, power at 80%, the necessary number of subjects will be 47. Taking into consideration of ineligible or discontinued subjects at approximately 10%, the target number of subjects was set to 52 (including subjects that received RD in the phase I part).

6.3 Discontinuation of entire clinical study or discontinuation of clinical study at a study site

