7.2.4.5 Level of significance, confidence coefficient

Significance level: Main analysis only, 5% (one-sided); other analyses, 5% (two-sided)

Confidence coefficient: Main analysis only, 90% (two-sided); other analyses, 95% (two-sided)

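### The 6-month imaging rule for the primary endpoint can fail subjects whose on-schedule scan shows no progression, and a misplaced censoring sentence and an undefined category leave its application unclear

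*SAP*

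**What the plan says.** **The classification rule.** SAP 7.2.4.1 (version 4.0) defines the primary endpoint as a crude proportion at enrollment + 24 weeks ± 2 weeks. "Subjects with no imaging data on progression at 6 months after enrollment", and those lost to follow-up, stay in the denominator but are not progression-free. Protocol 13.3.3.1 has the same rule and window.

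**The confirmation sentence.** Further down SAP 7.2.4.1, under the definition of progression, the PFS period of a surviving subject without progression is cut off on the last day progression-free status is confirmed. The next sentence reads: "Confirmation of progression-free status by imaging test or sample test is not mandatory, and clinical confirmation by outpatient medical examination, etc., will be allowed". In the protocol this text stands in 13.3.3.2, under the secondary endpoint PFS. In SAP 4.0 the cut-off rule is repeated under time-to-event PFS (7.2.4.2), but the clinical-confirmation sentence appears only in the primary endpoint section.

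**The count.** The main analysis in SAP 7.2.4.1 counts subjects with progression, without progression and *unconfirmed*. The last term is not defined.

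**The scan schedule.** Protocol 9.2.10 schedules imaging every 56 days from Course 1 Day 1, and Table 9.c allows ± 7 days. Protocol 8.1 has treatment start, in principle, within 14 days of entry. After treatment discontinuation, follow-up imaging is only as necessary (Tables 9.a and 9.b).

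**Sensitivity analysis.** SAP 7.4 varies only the handling of follow-up treatment.

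**The concern.** The endpoint window is counted from enrollment and the scans from the first treatment day. A subject who starts treatment late in the permitted period and is scanned late in the permitted range has no imaging inside the window, although every step followed the protocol. If that scan shows no PD, the subject was progression-free at 24 weeks, yet the imaging rule read plainly counts a failure.

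The section also leaves an analyst unsure what to do with a subject who was examined but not scanned at 6 months. The clinical-confirmation sentence is not marked as a censoring rule, and *unconfirmed* could be filled in either way. The trial is single-arm and open-label, so a gap left open would be settled by people who can see outcomes. Failing such subjects pushes the rate down. Counting clinically examined, unscanned subjects as progression-free could push it up.

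**Working it through.** **1. Reproduce the design.** Protocol 6.2.2.2 tests a threshold of 29% against an expected 48%. Its stated size is: "one-sided significant level at 5%, power at 80%, the necessary number of subjects will be 47". Take the smallest r with P(X ≥ r | n, 0.29) ≤ α; power is P(X ≥ r | n, 0.48), both exact binomial. For n = 47 and α = 0.05, r = 20, exact α = 0.0327 and power = 81.4%. The plan's 47 reproduces: it is the smallest n from which exact power stays at or above 80%. Allowing for about 10% losses, 47 × 1.10 = 51.7, which rounds up to the target of 52.

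**2. Baseline at n = 52.** The level is stated inconsistently. Protocol 6.2.2.2 and SAP 7.2.4.5 give one-sided 5%, while SAP 7.2.4.1 says "Significant level will be 2.5% (one-sided) in the main analysis". Both are shown.

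| One-sided α | Critical count | Exact α | Power at 48% |
|---|---|---|---|
| 5% | 22/52 | 0.0278 | 83.2% |
| 2.5% | 23/52 | 0.0139 | 75.2% |

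**3. Scan day against the window.** Count days from enrollment, with lag L = 0 to 14 and scan deviation S = −7 to +7.

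- Window: 168 ± 14 = days 154 to 182.
- Third scan: 168 + L + S, so from day 161 to day 168 + 14 + 7 = 189.
- Second scan: at the latest 112 + 14 + 7 = day 133, before the window.
- Fourth scan: at the earliest 224 − 7 = day 217, after the window.

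The third scan is therefore the only scheduled scan that can supply imaging in the window. It misses when L + S > 14, which needs a lag of at least 8 days.

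**4. How often.** The documents give no distribution of L or S. Assume both are uniform on whole days and independent, giving 15 × 15 = 225 combinations. Those with L + S > 14 number 1 + 2 + … + 7 = 28, and 28/225 = 12.4%. With lags of 7 days or less the figure is 0, so the true share depends on how quickly sites start treatment.

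**5. Effect on power.** If a fraction m of truly progression-free subjects is counted as failures, the effective rate is 0.48 × (1 − m). The value of m is assumed.

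| m | Effective rate | Power, n = 52, α 5% | Power, n = 52, α 2.5% |
|---|---|---|---|
| 0 | 0.480 | 83.2% | 75.2% |
| 2% | 0.470 | 79.4% | 70.6% |
| 5% | 0.456 | 73.0% | 63.1% |
| 10% | 0.432 | 60.4% | 49.3% |
| 12.4% | 0.420 | 53.7% | 42.5% |

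The last row applies the 12.4% of step 4 to every progression-free subject.

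**6. Direction of error.** At a true rate of 29% the imaging rule lowers the rejection probability: at α 5% and m = 10% it falls from 0.0278 to 0.0081. The cost is downward bias and lost power, not false positives.

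**The case against.** The strongest reply is that there is no contradiction. SAP 7.2.4.1 has one explicit rule for the binary endpoint. The clinical-confirmation sentence follows directly on the cut-off of the PFS period, and the protocol places it under time-to-event PFS. An unscanned subject fits naturally under *unconfirmed*, outside the numerator. Protocol 13.3.1 and SAP 7.1 require handling rules to be settled before data fixation, and protocol 13.0 gives the analysis to personnel independent of the sponsor. This stands in the main. A reader might infer that a subject examined but not scanned is both a failure and progression-free; the wording does not support that, because the sentence sets a censoring date and the specific rule prevails.

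A reader might also infer that one subject decides the result, since 22/52 gives p = 0.028 and 21/52 gives p = 0.052. That is true of any exact test at its critical value. The count falls exactly on 22 in only 7.9% of trials if the true rate is 48%, and at 2.5% the boundary is 23 against 22. It is not evidence of a defect.

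The 12% measures late scans, not subjects seen in clinic without a scan, and no figure for the latter is available. This is correct, and the 12% is used here only for late scans. Accepting a scan after the window is a change to the endpoint rule and not merely an explanation of it. That too is correct, and the cost below reflects it.

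The reply does not remove the mismatch between scan anchor and window, nor the missing definition of *unconfirmed*.

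**Conclusion.** The point holds in this form. The imaging rule probably governs, but applied as written it can count as failures subjects whose protocol-compliant scan, as late as day 189, shows no PD. The surrounding text does not say how to classify such subjects, nor those examined without a scan.

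The result is a primary rate biased down. At n = 52, failing 5% or 10% of truly progression-free subjects costs about 10 or 23 points of power at one-sided 5%, and about 12 or 26 points at 2.5%. These fractions are assumptions. The 12.4% for late scans rests on uniform lag and scan timing, and prompt starts would reduce it, to zero if no lag exceeded 7 days. What needs no assumption is that the schedule permits day 189 and the window ends at day 182.

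**What to change.** 1. In SAP 7.2.4.1, state that the cut-off and clinical-confirmation sentences set only the PFS censoring date, and move them to 7.2.4.2.
2. In SAP 7.2.4.1 and protocol 13.3.3.1, count a subject as progression-free when there is no clinical PD, radiological PD or death up to 24 weeks, and a scan in the window, or the first scan after it, shows no PD.
3. Define *unconfirmed* as subjects with neither such scan, and count them as failures.
4. In SAP 7.4, add one sensitivity analysis that counts clinically confirmed, unscanned subjects as progression-free.

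No new visits, scans or data items are needed: scan dates and the last confirmed progression-free date are already collected (protocol 9.2.10). The cost is a small wording amendment and one table. Protocol 6.4 lists a change in the efficacy evaluation method among the grounds for amendment, so item 2 should go through that route and be dated before data fixation. The 2.5% and 5% levels need reconciling separately, since they move the critical count at n = 52 from 23 to 22.
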